9.2 Subject Accountability

The number of subjects screened, randomized, receiving IP, and completing the study will be summarized by randomized treatment group. Key study dates for the first subject enrolled, last subject enrolled and last subject's end of study will be presented.

Study discontinuation and IP discontinuation will be tabulated separately by reasons for discontinuation, including due to COVID-19 impact if applicable.

The number and percent of subjects randomized will be tabulated by study site, the stratification factors.

The number of subjects included in and excluded from each analysis set and reason for exclusion will also be summarized.

9.3 Important Protocol Deviations

Important Protocol Deviations (IPDs) categories are defined by the study team before the first subject's initial visit and updated during the IPD reviews throughout the study prior to

database lock. These definitions of IPD categories, subcategory codes, and descriptions will be used during the course of the study. Eligibility deviations are defined in the protocol.

The number of subjects reporting Protocol Deviations due to COVID-19 impact will be summarized in a table. A Protocol Deviation listing of subjects impacted due to COVID-19 will also be provided.

9.4 Demographic and Baseline Characteristics

All baseline tables will be summarized by randomized treatment group and overall using descriptive statistics. Baseline tables will summarize demographics, baseline characteristics, targeted medical history, and lipid regulating medication. If multiple races have been reported for a subject, the subject will be categorized as multiple race. Difference in stratum assignment between IVRS/IWRS stratum and data-derived stratum will be tabulated.

9.5 Efficacy Analyses

9.5.1 Analyses of Primary Efficacy Endpoint

To assess the primary endpoint of the mean percent change from baseline at week 36 in Lp(a), a repeated measures linear mixed effects model including terms for treatment group, stratification factors, scheduled visit and the interaction of treatment group with scheduled visit will be used. The least squares means (LS means) by treatment group and the treatment difference (olpasiran - placebo) at week 36 based on the model above will be summarized. The Hochberg procedure will be used to control the type I error for multiple comparisons between active and placebo groups.

To evaluate the robustness of the analysis results, sensitivity analyses will be performed as follow:

- The primary analysis will be repeated using CAS.
- Non-parametric analyses (Quade test) will be performed based on CAS
- To evaluate the impact of missing data, multiple imputation for subjects who discontinue IP with missing endpoint data:
 - It will be assumed that the missing percent change values will be normally distributed with a mean zero and a variance-covariance matrix the same as the observed variance-covariance matrix from subjects in the placebo group who did not discontinue IP with missing endpoint data.
 - If there is sufficient number of subjects in each treatment group who discontinue IP but have non-missing endpoint data, an additional multiple imputation will be carried out utilizing the information from these subjects to impute the missing data for subjects who discontinue IP and have missing endpoint data.

Additional analysis for percent change in Lp(a) from baseline at week 36 of all dose groups (Q12W and Q24W) will be performed using Multiple Comparison Procedure - Modelling (MCP-Mod) methodology (Bretz et al, 2005). MCP-Mod is a hybrid approach that combines hypothesis testing and modeling in a structured manner to analyze phase 2 dose-ranging studies with the purpose of finding target dose(s) of interest and provide guidance for suitable dose(s) entering the confirmatory phase 3 trials. The first step of the procedure (MCP-step) is used to assess presence of a dose response signal using a trend test deducted from a set of prespecified candidate models. The prespecified candidate

dose response models will be selected based on the known pharmacology and Lp(a) reduction of Olpasiran from phase I trials. The second step (Mod-step) relies on parametric modeling or model averaging to find the “optimal” dose for confirmatory trials. MCP-Mod method is found more effective than pairwise comparison due to its ability to utilize all available data from the continuum of active doses and placebo to estimate a parametric dose response curve which allows for interpolation and extrapolation of effect across a range of doses (Dinko Rekić et al, 2015).

Covariate analyses of the primary endpoint will be performed. Baseline covariates listed in Section 4.1 in their original format, will be included one at a time, in the repeated measures model used in the primary analysis.

Subgroup analyses on the primary efficacy endpoint will be conducted using the subgroups specified in Section 4.2. Treatment effect differences among subgroups, which represent subgroup by treatment interactions, will be estimated and tested based on statistics from the subgroup repeated measures models.

For covariate and subgroup analyses, the data-derived stratification factors will be used.

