Table 1-2. Schedule of Activities-PK Sub-study

PROCEDURE	Screening	Week 1 (Dose 1)		Week 24 (Dose 2 [Q24W], Dose 3 [Q12W])	
		6 to 12 hrs post-dose	24 to 72 hrs post-dose	6 hr to 12 hrs post dose	24 hrs to 72 hrs post dose
GENERAL AND SAFETY ASSESSMENTS					
PK Sub-study Informed Consent	X				
Adverse events		X	X	X	X
Serious adverse events ^a	X	X	X	X	X
Concomitant therapies review		X	X	X	X
PHARMACOKINETIC ASSESSMENTS					
Olpasiran serum PK ^b		X	X	X	X

Hr(s) = hour(s); PK = pharmacokinetics; Q12W = once every 12 weeks; Q24W = once every 24 weeks

^a After end of study, if the investigator becomes aware of serious adverse events suspected to be related to investigational product, then these serious adverse events will be reported to Amgen. Please refer to Section 8.2.4.1.3 for additional details.

^b PK sub-study subjects will also have the required PK samples drawn as part of the main study (refer to Table 1-1 for time points).

2. Introduction

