
 • To evaluate the effect of olpasiran administered SC once every 24 weeks (Q24W) compared with olpasiran administered SC Q12W and placebo, on: 
 - percent change from baseline in Lp(a) - percent change from baseline in LDL-C - percent change from baseline in ApoB - achievement of Lp(a) < 125 nmol/L - achievement of Lp(a) < 100 nmol/L - achievement of Lp(a) < 75 nmol/L - achievement of Lp(a) < 50 nmol/L 	
For the olpasiran SC Q24W group:
 
 • Percent change from baseline at each scheduled visit, in: 
 - Lp(a) - LDL-C - ApoB • Achievement at each scheduled visit of the following: 
 - Lp(a) < 125 nmol/L - Lp(a) < 100 nmol/L - Lp(a) < 75 nmol/L - Lp(a) < 50 nmol/L

Objectives	Endpoints

Exploratory
	

 • To estimate cardiovascular event rates in subjects treated with olpasiran, including aggregated exploratory analyses across the olpasiran program 	
 • Adjudicated events

 • To describe the effect of olpasiran of quality of life (QoL) measures as assessed using the PROMIS Global Health 	
 • Change from baseline in PROMIS Global Health measures at each scheduled visit

 • To evaluate the effect of olpasiran administered SC on inflammatory biomarkers 	
 • Change from baseline at week 48 in: 
 - high sensitivity C-reactive protein (hs-CRP) - high sensitivity Interleukin 6 (hs-IL-6)

To assess the anti-olpasiran antibody response	
Anti-olpasiran antibody formation, if tested
Safety	

To evaluate the safety and tolerability of olpasiran administered SC compared with placebo in subjects with elevated Lp(a)	
Treatment emergent adverse eventsClinically significant safety laboratory values and vital signs at each scheduled visit

4. Study Design

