6.1 Treatment(s) Administered

6.1.1 Investigational Products

Table 6-1. Study Treatments

Study Treatment Name	Amgen Investigational Product: ^{a,b} olpasiran		Placebo
Dosage Formulation	The final container is a 2R vial size. Type I glass vial and contains 1 mL deliverable volume of olpasiran (1 mL vial target fill volume).		Placebo will be presented in identical containers, and stored/package the same as olpasiran
Unit Dose Strength(s)/ Dosage Level(s) and Dosage Frequency	
 • Treatment Group 1: 10 mg Q12W • Treatment Group 2: 75 mg Q12W • Treatment Group 3: 225 mg Q12W • Treatment Group 4: 225 mg Q24W 		
 • Treatment Group 5: Placebo Q12W
Route of Administration	SC injection		
Accountability	The volume, start date, start time, injection site, and box number(s) of investigational product are to be recorded on each subject's CRF.		
Dosing Instructions	Study treatment are to be administered at study visits by authorized investigational site study staff per the investigational product instructional manual (IPIM). Olpasiran administration should be completed after all study visit activities including pre-dose PK blood draws have been performed, but prior to the 1 hour and 3 hour post-dose PK measurements. An observation period of 1-hour will occur after each injection of study treatment.		

CRF = case report form; PK = pharmacokinetic; Q12W = once every 12 weeks; Q24W = once every 24 weeks; SC = subcutaneous

^a Olpasiran will be manufactured and packaged by Amgen and distributed using Amgen clinical study drug distribution procedures.

^b In order to maintain blinding, placebo will administered to some olpasiran treatment groups, as applicable.

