
 • To characterize the pharmacokinetic (PK) properties of olpasiran 	
 • PK parameters for olpasiran including, but not limited to, maximum observed concentration (C_{max}), and the area under the concentration time curve (AUC)

Estimands for Secondary Endpoints

The estimands for the secondary endpoints in Lp(a), LDL-C, and ApoB are the differences between each olpasiran group and placebo in the mean percent change from baseline in:

- Lp(a) at week 48
- LDL-C at week 36
- LDL-C at week 48
- ApoB at week 36
- ApoB at week 48

For adults with atherosclerotic cardiovascular disease and elevated Lp(a) who are randomized and received at least 1 dose of investigational product, regardless of discontinuation of investigational product and excluded medication(s) taken during the study.

Exploratory

 • To evaluate the effect of olpasiran administered SC Q12W compared with placebo, on: 
 – percent change from baseline in Lp(a) – percent change from baseline in LDL-C – percent change from baseline in ApoB – achievement of Lp(a) < 125 nmol/L – achievement of Lp(a) < 100 nmol/L – achievement of Lp(a) < 75 nmol/L – achievement of Lp(a) < 50 nmol/L 	
 • Percent change from baseline at each scheduled visit, except weeks 36 and 48, in: 
 – Lp(a) – LDL-C – ApoB • Achievement at each scheduled visit of the following: 
 – Lp(a) < 125 nmol/L – Lp(a) < 100 nmol/L – Lp(a) < 75 nmol/L – Lp(a) < 50 nmol/L

 • To evaluate the effect of olpasiran administered SC Q24W compared with olpasiran administered SC Q12W and placebo, on: 
 – percent change from baseline in Lp(a) – percent change from baseline in LDL-C – percent change from baseline in ApoB – achievement of Lp(a) < 125 nmol/L 	
For the olpasiran SC Q24W group:
 
 • Percent change from baseline at each scheduled visit, in: 
 – Lp(a) – LDL-C – ApoB • Achievement at each scheduled visit of the following:

 - achievement of Lp(a) < 100 nmol/L - achievement of Lp(a) < 75 nmol/L - achievement of Lp(a) < 50 nmol/L 	
 - Lp(a) < 125 nmol/L - Lp(a) < 100 nmol/L - Lp(a) < 75 nmol/L - Lp(a) < 50 nmol/L

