Efficacy	
 • Repeated measures model for primary endpoint, secondary endpoints defined at week 36, and exploratory endpoints of percent change from baseline in Lp(a), LDL-C and ApoB up to week 36. • Multiplicity adjustment for primary endpoint, as described above in Multiplicity Adjustment Method • Sensitivity analysis for primary endpoint using non-parametric (Quade test) approach based on CAS • Cochran-Mantel Haenszel (CMH) test adjusted by the stratification factors will be used for exploratory endpoints of Lp(a) achievements 	
 • Repeated measures model for primary endpoint, secondary endpoints defined at week 36 and week 48 and exploratory endpoints of percent change from baseline in Lp(a), LDL-C and ApoB up to week 48. Testing is performed up to week 48. • Multiplicity adjustment for primary endpoint, as described above in Multiplicity Adjustment Method • Sensitivity analysis for primary endpoint using non-parametric (Quade test) approach based on CAS • Cochran-Mantel Haenszel (CMH) test adjusted by the stratification factors will 	
 • Descriptive summary for efficacy endpoints in the extended follow-up period

	
(including achievement of Lp(a) < 125nmol/L) up to week 36
 
 • Descriptive summary for all efficacy endpoints by period (ie. Treatment period and extended safety follow-up period) 	
be used for exploratory endpoints of Lp(a) achievements (including achievement of Lp(a) < 125nmol/L) up to week 48
 
 • Descriptive summary for all efficacy endpoints by period (ie. Treatment period and extended safety follow-up period) 	
Safety	
 • Summary by actual treatment group by period (ie. Treatment period and extended safety follow-up period) 	
 • Summary by actual treatment group by period (ie. Treatment period and extended safety follow-up period) 	
 • Summary by actual treatment group in the extended follow-up period

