9.5.3 Analyses of Exploratory Efficacy Endpoint(s)

Exploratory endpoints of percent change from baseline at scheduled visits in Lp(a), LDL-C and ApoB will be analyzed using repeated measures linear effects model including terms for treatment group, stratification factors, scheduled visit and the interaction of treatment group with scheduled visit will be used; and achievements of Lp(a) at scheduled visits (including achievement of Lp(a) < 125nmol/L) will be analyzed using CMH test as specified in Table 2. Subject incidence of positively adjudicated events (overall and by event type as defined in protocol) and change from baseline in PROMIS Global Health measures at scheduled visits will be summarized by treatment group using descriptive statistics.

Descriptive summary for non-HDL-C, HDL-C, VLDL-C and Triglycerides will be provided by scheduled visits.

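### Does the SAP need to name a Q24W-versus-Q12W contrast and state how the Q24W arm is coded in the week-36 MCP-Mod analysis?

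*SAP*

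**What the plan says.** The exploratory objective in SAP 2.1 reads "To evaluate the effect of olpasiran administered SC Q24W compared with olpasiran administered SC Q12W and placebo", and Protocol Section 3 uses the same comparison ("compared with olpasiran administered SC Q12W and placebo"). For the Q24W group, both documents define the endpoints at each scheduled visit: percent change in Lp(a), LDL-C and ApoB, and four Lp(a) thresholds.

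SAP 9.5.3 gives the method: "percent change from baseline at scheduled visits in Lp(a), LDL-C and ApoB will be analyzed using repeated measures linear effects model", with treatment group, stratification factors, visit and treatment-by-visit interaction. The thresholds get a CMH test. In Table 2 of SAP 9.1, the end-of-treatment analysis covers "exploratory endpoints of percent change from baseline in Lp(a), LDL-C and ApoB up to week 48".

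The difference spelled out in SAP 9.5.1 is against placebo: "the treatment difference (olpasiran - placebo) at week 36 based on the model above will be summarized". SAP 9.5.2 treats the week-48 secondary endpoints similarly. SAP 9.1 limits the Hochberg comparison to the Q12W groups and placebo, and classes the Q24W result as exploratory.

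For MCP-Mod, SAP 9.5.1 says: "Additional analysis for percent change in Lp(a) from baseline at week 36 of all dose groups (Q12W and Q24W) will be performed using" that method. Candidate models are to be chosen from phase 1 pharmacology. No dose scale is given, although Protocol 9.4.2.2 said the SAP would supply the details.

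On timing, Protocol Table 1-2 labels the second sampled dosing visit "Week 24 (Dose 2 [Q24W], Dose 3 [Q12W". Protocol Table 6-1 says "Olpasiran administration should be completed after all study visit activities including pre-dose PK blood draws have been performed", and the week-36 Lp(a) sample is scheduled pre-dose in Table 1-1.

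**The concern.** Three features together look like a gap. First, a stated objective has no written contrast: there are three Q12W arms, and the SAP does not say which one Q24W is set against or that the difference will be reported. A comparator picked after unblinding could be picked to suit.

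Second, Protocol 4.3 says the Q24W arm is there to study Lp(a) lowering over the whole 6-month interval with repeated dosing. Week 36 falls halfway through that interval, so a reader could take a mid-interval value as evidence of 24-week durability.

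Third, MCP-Mod needs a number on the dose axis for each arm. Two arms give 225 mg per injection at different frequencies, and the SAP does not say whether they share a dose value. What is at stake is how the Q24W regimen is read when phase 3 doses are chosen.

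**Working it through.** **1. The plan's own figure.** SAP 3.2 gives at least 90% power with 48 per arm, SD 30, a difference of 25 points, 5% dropout and Bonferroni. Evaluable n = 48 × 0.95 = 45.6, and SE = 30 × √(2/45.6) = 6.28. The number of comparisons and the sidedness are not stated, so I took two-sided tests over 3 or 4 comparisons.

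- Four comparisons (0.0125 each): power = Φ(25/6.28 − 2.498) = Φ(1.48) = 93.1%.
- Three comparisons (0.0167 each): power = Φ(25/6.28 − 2.394) = Φ(1.585) = 94.4%.

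The figure reproduces. It concerns olpasiran against placebo. The documents give no figure for Q24W against Q12W.

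**2. Where each visit falls.** Active doses are at weeks 0, 12, 24 and 36 (Q12W) and at weeks 0 and 24 (Q24W). Samples on dosing days are taken before the injection.

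| Visit | Weeks since last active dose, Q12W / Q24W | Active doses before sample, Q12W / Q24W |
|---|---|---|
| Week 24 | 12 / 24 | 2 / 1 |
| Week 36 | 12 / 12 | 3 / 2 |
| Week 48 | 12 / 24 | 4 / 2 |

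Week 36 is the end of the interval for Q12W and the midpoint for Q24W. Within the treatment period, week 48 is the only end-of-interval visit for Q24W after more than one active dose.

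**3. What is actually left open.** SAP Appendix A lists 13 post-baseline Lp(a) visits in the treatment period (day 2, and weeks 4 to 48 every 4 weeks). Multiplying by three Q12W arms gives 39 contrasts, but that count overstates the freedom. The endpoint is defined at every scheduled visit and the model is run to week 48, so the visits are included, not undecided. The open item is the comparator, with three possibilities, of which one has the same dose per injection.

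**4. Precision of the same-dose contrast.** Half-width = 1.96 × SD × √(2/n), taking n = 58 × 0.95 ≈ 55 or 48 × 0.95 ≈ 46.

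- SD 30: 1.96 × 5.72 = 11.2 (n = 55); 1.96 × 6.26 = 12.3 (n = 46).
- SD 15 (my assumption for active arms): 5.6 and 6.1.

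This is an estimate from a model already planned. Naming it would change neither its value nor its precision.

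**5. Dose coding.** Before the week-36 sample, the 225 mg Q12W arm has had 3 × 225 = 675 mg and the Q24W arm 2 × 225 = 450 mg. Q24W could be coded as 225 (per injection), 450/3 = 150 (per 12 weeks to date) or 225/2 = 112.5 (long-run average per 12 weeks).

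As an illustration, I fitted reduction = Emax × d/(ED50 + d) without weights to 0% (placebo), 77% (10 mg, Protocol 4.3), 93.2% (75 mg) and 95.2% (225 mg Q12W). The last two come from the Protocol 4.3 responder rates of 94% and 98%, under an assumed common log-normal spread. That spread is ln(0.20/0.23) divided by the 42nd normal percentile, which is 0.692. I then added Q24W and recorded the shift in the dose giving a 90% reduction:

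| Q24W reduction entered | Coded 112.5 | Coded 225 |
|---|---|---|
| 95.2% (equal to 225 mg Q12W) | −3.9% | +0.1% |
| 93.2% (2 points lower) | +4.3% | +9.1% |
| 88% (modelled median, Protocol 4.3) | about +40% | about +52% |

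The protocol does not say when in the interval the 88% applies. The shift depends almost wholly on the value entered, so this exercise shows neither a small nor a large effect.

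**The case for a change.** The best argument for a change is that exploratory status does not excuse leaving a stated objective without a stated comparison. A treatment-by-visit term makes the contrast estimable, but that is not the same as prespecifying it. The protocol promised MCP-Mod details in the SAP and the coding is absent, so two analysts could fit different curves from the same text. A few sentences would settle both points, with no new visits, samples or subjects.

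Part of this stands. The comparator and the coding are not written down, and the coding is the weightier omission because the last row of the table does not rule out a sizeable effect.

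The rest does not carry. The worry about a week-36 comparison is hypothetical, because the plan gives the Q24W-versus-Q12W objective no preferred visit; week 36 belongs to the primary endpoint and to MCP-Mod. Nor is week 36 an unfair visit: both 225 mg arms are equally far from their last active dose, and mid-interval data are part of an arm meant to describe the whole interval. That the value is mid-interval follows directly from the dosing schedule. MCP-Mod is also not the only input to dose selection: SAP 3.1 assigns that use to the interim analysis, and Protocol 6.4.2.2 describes an exposure-response analysis with its own plan.

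**Conclusion.** No change to the plan is needed. The effect on the primary test and its multiplicity control is nil, because Q24W is outside the Hochberg family. No bias in the week-36 estimate has been shown: it is valid for week 36. The analysis that answers the Q24W objective is already in the SAP at every visit to week 48, including the visit that ends the second active Q24W interval. A competent analyst would take 225 mg Q12W as the comparator, report the difference with its interval (about ±11 to ±12 points at the planning SD), and state the MCP-Mod coding alongside the fit.

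This rests on three things: that Q24W results stay exploratory, that the by-visit model is reported as Table 2 says, and that the curve is not read alone as evidence on the 24-week interval. The size of the coding effect remains unknown, because the documents give no week-36 value for the Q24W arm.

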4.3 Justification for Investigational Product Dose

Investigational product dose ranges were selected based on available data from phase 1 Study 20170544 and the additional following considerations:

- General understanding of safety regarding oligonucleotide-based therapeutics, ie, antisense oligonucleotide and siRNA therapeutics and their mechanism of action.
- Lp(a) reductions of $\geq 80\%$ from baseline are being targeted because this level of reduction is anticipated to be required to observe cardiovascular benefit in patients with atherosclerotic cardiovascular disease.
- Olpasiran PK/PD modelling and simulation results based on data from Study 20170544 indicate that:
 - A low dose of 10 mg administered Q12W will provide target ($\geq 80\%$) Lp(a) suppression in approximately half (42%) of subjects with baseline Lp(a) ≥ 150 nmol/L by month 12. Despite median Lp(a) % reductions from baseline of approximately 77% at months 6 and 12, only 41% and 64% of these subjects will achieve Lp(a) values of ≤ 50 nmol/L by month 12. Therefore, the 10 mg dose will provide additional PK and Lp(a) data within the lower dynamic range of the olpasiran exposure-response relationship and help support selection of the phase 3 dose in the target patient population.
 - An intermediate dose of 75 mg administered Q12W was selected as it is anticipated to provide target (80%) Lp(a) suppression from baseline within 2 to 3 doses in the majority (94%) of subjects by month 12. Furthermore, approximately 90% of subjects are expected to achieve Lp(a) ≤ 50 nmol/L, which may support selection of this dose for phase 3 evaluation.
 - A high dose of 225 mg Q12W is expected to provide a similar degree of Lp(a) suppression ($\geq 80\%$) in the majority of subjects (98%), but with a greater proportion of subjects (96%) achieving reductions of Lp(a) ≤ 50 nmol/L by month 12. Given that the magnitude and durability of Lp(a) suppression appears to increase with dose, the 225 mg dose will also provide greater magnitudes of Lp(a) suppression with multiple dosing.
- A frequency of Q12W dosing was selected for the above doses based on the durability of Lp(a) response over time and to ensure target suppression levels are maintained throughout the entire dosing interval in the majority ($\geq 90\%$) of subjects with elevated Lp(a) levels > 150 nmol/L.

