9.4.2.2 Efficacy Analyses

Endpoint	Statistical Analysis Methods
Primary	
The analysis of percent change from baseline in Lp(a) at week 36 will be performed when all randomized subjects have had the opportunity to complete the week 36 assessments or have early terminated. A repeated measures linear effects model including terms for treatment group, stratification factors, scheduled visit and the interaction of treatment with scheduled visit will be used. The least squares means (LS means) by treatment group and the treatment difference (olpasiran - placebo) based on the model above will be summarized. The Hochberg procedure will be used to control the type I error for multiple comparisons between active and placebo arms.
 
A sensitivity analysis will be performed using multiple imputation to impute missing data. Details of the imputation rules for the sensitivity analysis will be provided in the SAP.
 
Additional analysis of the primary endpoint will be explored using Multiple Comparison Procedure - Modelling (MCP-Mod) methodology (Bretz et al, 2005). Details will be provided in the SAP.

Secondary	
Analysis of the secondary endpoints will be performed when all randomized subjects have had opportunity to complete week 48 assessments or have early terminated.
 
Analysis of the secondary endpoints (including percent change from baseline at week 36 in ApoB and LDL-C, and percent change from baseline at week 48 in ApoB, Lp(a) and LDL-C) will be performed similarly to the analysis of the primary endpoint.

Exploratory	Will be described in the statistical analysis plan finalized before database lock

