2.1 Objectives and Endpoints/Estimands

Objectives	Endpoints
Primary	

 • To evaluate the effect of olpasiran administered subcutaneous (SC) every 12 weeks (Q12W) compared with placebo, on percent change from baseline in Lp(a) after 36 weeks of treatment 	
 • Percent change in Lp(a) from baseline at week 36
Primary Estimand	

The primary estimand consists of:
 
 • The target population, which is adults with atherosclerotic cardiovascular disease and elevated Lp(a) • The primary variable, which is percent change from baseline in Lp(a) at week 36 • The intercurrent events which are the discontinuation of investigational product and excluded medication(s) taken during study. For the primary estimand, the treatment effect will be estimated in subjects who are randomized and received at least 1 dose of investigational product regardless of the occurrence of these intercurrent events • The summary measure, which is the difference between olpasiran and placebo in the mean percent change from baseline in Lp(a) at week 36 • The treatments to be compared are each olpasiran group vs. placebo 
The primary estimand is the difference between each olpasiran group and placebo in the mean percent change from baseline in Lp(a) at week 36 in adults with atherosclerotic cardiovascular disease and with elevated Lp(a) who are randomized and received at least 1 dose of investigational product, regardless of discontinuation of investigational product and excluded medication(s) taken during the study.
	
Secondary	

 • To evaluate the effect of olpasiran administered SC Q12W compared with placebo, on percent change from baseline in: 
 – Lp(a) after 48 weeks of treatment 	
 • Percent change from baseline in: 
 – Lp(a) at week 48 – LDL-C at week 36 and week 48 – ApoB at week 36 and week 48

 – Low- density lipoprotein cholesterol (LDL-C) after 36 and 48 weeks of treatment – Apolipoprotein(B) (ApoB) after 36 and 48 weeks of treatment 	

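### Does SAP 9.5.1 leave MCP-Mod too loosely specified to guide dose choice?

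*SAP*

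**What the plan says.** Protocol 9.4.2.2, in the row for the primary endpoint, says that the endpoint will also be explored with MCP-Mod and adds: "Details will be provided in the SAP".

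SAP 9.5.1 takes this up. It applies the method to "percent change in Lp(a) from baseline at week 36 of all dose groups (Q12W and Q24W) will be performed", cites the method paper, and describes the two steps:

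- **Purpose.** MCP-Mod is introduced as a way to analyse phase 2 dose-ranging studies "with the purpose of finding target dose(s) of interest and provide guidance for suitable dose(s) entering the confirmatory phase 3 trials".
- **MCP step.** The candidate models are called prespecified. The "dose response models will be selected based on the known pharmacology and Lp(a) reduction of Olpasiran from phase I trials".
- **Mod step.** This "relies on parametric modeling or model averaging to find the" best dose for confirmatory trials.

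Two other places bear on the target. Protocol 4.3 says that reductions of at least 80% "from baseline are being targeted because this level of reduction is anticipated to be required to observe cardiovascular benefit". The primary estimand in SAP 2.1 is instead "the difference between olpasiran and placebo in the mean percent change from baseline in Lp(a) at week 36".

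SAP Table 2 summarises the efficacy analyses at each snapshot, starting with "Repeated measures model for primary endpoint, secondary endpoints defined at week 36, and exploratory endpoints". It does not mention MCP-Mod.

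**The concern.** The protocol promises details and the SAP gives a textbook description. Five things that determine the output are missing: the candidate models, the dose scale, where 225 mg Q24W sits relative to 225 mg Q12W, the target effect, and whether one model is selected or several are averaged. Without the candidate shapes, the trend-test contrasts cannot be computed.

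The Q24W arm raises a genuine coding question. At the week-36 pre-dose sample, both 225 mg arms are 12 weeks past their last active dose, but the Q12W arm has had three doses (day 1, weeks 12 and 24) and the Q24W arm two (day 1 and week 24).

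The SAP ties the method to the choice of phase 3 doses, and Protocol 6.4.2.2 treats some biostatistics staff as unblinded during conduct. If the choices were made after seeing results, the models could not be shown to have been prespecified, and the reported target dose could reflect a convenient choice.

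**Working it through.** The MCP-Mod text states no figure to reproduce. The check has two parts: what the documents already settle, and how much the open items could move the result.

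**What the documents settle**

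1. *Status.* SAP 9.1 applies Hochberg to the primary endpoint in the Q12W groups and makes Q24W exploratory. MCP-Mod is in neither the Hochberg procedure nor the primary model.
2. *Timing.* Protocol 9.4.2.2 places MCP-Mod in the Primary row, which is performed once all subjects have had the opportunity to complete week 36. Table 2 also omits the multiple imputation, the repeat of the primary model in completers, and the covariate and subgroup analyses, all planned in SAP 9.5.1. It is a summary, so absence from it says nothing particular about MCP-Mod.
3. *Source of the models.* They are to come from pharmacology and phase 1 data, not from this trial.
4. *Target.* Protocol 2.1 and 4.3 both express the 80% reduction relative to baseline.
5. *Role in dose choice.* The analyses that the protocol names as support for phase 3 dose selection are the administrative interim (4.1 and Appendix 3) and the exposure-response analysis, which has its own plan (6.4.2.2).

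**How much the open items move an illustrative fit**

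Inputs from the documents: placebo -3 (sample size section); 10 mg -77 and 225 mg Q24W -88 (simulated medians in Protocol 4.3, used here as means); SD 30; 58 per arm with 5% drop-out, so 58 × 0.95 ≈ 55. Assumed: means for 75 and 225 mg Q12W of (-93, -97), (-90, -95) or (-88, -95), and -93 as an alternative for Q24W. The results are positions on a fitted curve, not proposed doses.

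Model: E(d) = E0 + Emax·d/(ED50 + d). The dose reaching effect t is d = ED50·(t − E0)/(Emax − (t − E0)).

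With (-90, -95), Q24W -88 and coding 225 mg, least squares gives E0 = -3.00, Emax = -89.34, ED50 = 2.07. For t = -80: 2.072 × 77/12.342 = 12.9. For t = -83 (80 points below a placebo mean of -3): 2.072 × 80/9.342 = 17.7.

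| Open item | Result at the 80% target |
|---|---|
| Q24W coded 225, 150 or 112.5 mg, Q24W mean -88 | 12.4/12.6/12.7; 12.9/13.0/13.1; 13.3/13.3/13.4 (2% or less) |
| Target -80 or -83 | smallest shift 12.3 to 15.5, largest 13.3 to 18.5 (about 3 to 5 mg) |
| Sampling error, Emax, 5th to 95th percentile | about 7 to 19 mg |

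At -85 the Emax coding effect is also 2% or less. At -90 it is 4% to 18%, but neither -85 nor -90 is a target stated in the documents.

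*Candidate shape.* Sigmoid Emax against Emax, 300 simulated trials for each of two sets of means, (-3, -77, -93, -97, -93) and (-3, -77, -90, -95, -93). The median absolute ratio is 1.11 and 1.15 at -80, and 1.33 and 1.42 at -85. That ratio cannot fall below 1, so it counts noise as difference. The signed medians are 0.99 and 1.05 at -80, and 0.98 and 1.23 at -85. The Hill parameter lay on its imposed limit (0.5 or 4) in 64% and 73% of trials: with Q24W coded 225 mg there are four distinct dose levels for a four-parameter curve.

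**The case for a change.** The strongest case for a change is that a poor choice can move the answer a great deal. A sigmoid Emax fit at -85 goes from 22.7 to 40.0 on Q24W coding alone (means -90, -95, Q24W -88; 225 against 112.5 mg). The linear-model contrast weight for Q24W falls from 0.529 to 0.153. A log-linear curve reaches -80 at 61.5, where Emax gives 12.9. Sampling error appears in a confidence interval, whereas an unrecorded choice of model does not. Writing the choices down would cost little.

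Part of this stands: the choices are not neutral, and the SAP does not record them. But the extreme figures come from curves that a competent analyst would not rely on. The log-linear fit passes through -80 at 61.5 and -85 at 85.9 on a log(d + 1) scale, so its slope is -5/(4.465 − 4.135) ≈ -15.1 per log unit. At 10 mg it predicts -80 + 15.1 × (4.135 − 2.398) ≈ -54, against an arm mean of -77. The miss of about 23 points compares with a standard error of 30/√55 = 4.05, so any fit-based selection or weighting would discount that curve. The sigmoid result comes from a four-parameter curve on four or five dose points, at a target that the documents do not set.

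The blinding argument adds little. Protocol 6.4.2.2 limits those staff to the sample types they handle and keeps them out of conduct decisions, and no document says that they choose the models. A Q12W-only fit as a safeguard would be a matter of preference, and would leave only four dose levels.

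**Conclusion.** The five items are absent from SAP 9.5.1, and the protocol said that they would be there. This is missing detail in an additional, exploratory analysis; no stated rule gives a wrong answer. The primary test, the multiplicity control and the week-36 timing are unaffected. The SAP already requires models fixed ahead of the fit from phase 1 information, and the analysts cannot run the trend test without settling the shapes and the dose scale. Nor is there a demonstrably better method to put in place of the one described; the most that could be asked is fuller documentation of it.

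At the one target the documents state, the coding effect is 2% or less under Emax. The choice of reference is worth about 3 to 5 mg, against a sampling range of about 7 to 19 mg. These figures rest on simulated medians used as means, on assumed means for 75 and 225 mg Q12W, and on an Emax shape. Under other shapes and deeper targets the effects are larger but weakly identified. No change to the plan follows.
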